# Retention: Role of All Study Personnel

All members of the study team will be responsible for ensuring participant retention throughout the duration of the study. [name] will manage participant recruitment, with the assistance of [name], and communicate with study physicians about safety considerations during enrollment and the intervention. [name], who conducts research in knee OA individuals, will advise on strategies for recruitment and retention.

Monthly meetings of the Research Team will be coordinated by [name]. Monthly meetings will ensure that the described aims are completed in a timely fashion and that the overall direction of the project is guided by recent discoveries in each of the aims. [name] will lead monthly meetings of the research team and Dr.

[name] will be responsible for organizing, scheduling and facilitating the meetings. The meetings will provide an opportunity to discuss recent progress, scientific design, data interpretation and future directions. Inclusion of additional members at the monthly meetings (for advice and scientific expertise) will be agreed upon by both [name] and [name]. Drs. [name] and [name] currently have weekly communications, providing a foundation for timely interaction and trouble-shooting of issues that may arise.

[name] will manage the training of the laboratory team with the HIIT protocol and laboratory testing, provide checks to confirm protocol and testing fidelity, and oversee the one-on-one HIIT instruction. [name] will hold bi-monthly meetings with the laboratory team in which scientific and project issues will be discussed. All members of the research team will be made aware that retention efforts begin with participant recruitment, and informed consent is an ongoing process throughout the entire duration of the study. During each meeting all members of the research team will be reminded to address all study participants with congeniality, respectfulness and friendliness during each interaction with a participant or potential participant. Additionally, all members of the research team will be asked to ensure all questions from the study participants and family members of the study participants are completely answered throughout each interaction with study participants.

Three participants per month are expected to be enrolled with at least 80% retention during the study period. As part of Aim 1, adherence to and tolerability of HIIT, acceptability, and recruitment and retention rates of patients through 6- and 12-week assessments will be determined. This will be determined as the percent of participants that screen into the study versus those approached and the percent of participants retained at the 6- and 12-week post-tests. Frequency and reasons for initial refusal, ineligibility, and drop out will be collected. Adherence and tolerability will be evaluated based on number of sessions attended/completed, modifications, such as change in mode; number of training days per week; recovery days needed between sessions to complete training, and severity of pain on a scale of 0-10 (no pain-extreme pain) during and after exercise as a measure of tolerability. If the HIIT intervention is shown to be well-tolerated and promising, results of this preliminary study will lay the foundation for a large randomized controlled trial to establish the efficacy of HIIT as a revolutionary approach for enhancing the rehabilitation and management of knee OA.

#### Enhancing Participants Understanding of the Study

During the initial meeting with a potential study participant the Research Assistant or Study Coordinator will be responsible for describing all aspects of the study in detail in order to ensure the participant completely understands the scope of the study and what will be required of each participant. The Research Assistant will provide the participant with a copy of the informed consent form, and will talk through each component with the participant. The participant will be able to ask any questions necessary in order to ensure the participant is informed about the purpose of the study and what he/she will be asked to complete. Additionally, study participants will be made aware they have an active role in the research study and are a valuable part of the research team. Throughout the course of the study all participants will have the opportunity to meet directly with the Research Assistant, Study Coordinator or Principal Investigator each week in order to ask any questions the participant may have.

All clinical and functional assessments will be described and demonstrated before the participant is asked to complete them; participants may choose not to engage in a particular assessment if they anticipate it will not be tolerable, and they may ask to stop an assessment at any time.

Determining Participant Satisfaction

As part of Aim 1, the physical activity enjoyment scale will be given on each training day, to assess participant enjoyment of exercise. After completion of the HIIT program, a structured one-on-one interview will occur with participants. The interview will be used to learn about barriers and concerns they experienced with regard to the current training protocol; preference of exercise mode and instruction; and opinions on what information participants would find helpful to transition to an at-home and or independent program. While we do not intend to formally analyze the interview responses, we do anticipate that they will be useful for refining our intervention program for inclusion and development of a home-based component for future trials.

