# Aim 2 Analyses

All available data from all enrolled participants, regardless of extent of adherence to HIIT, will be descriptively summarized in tables and graphs. Longitudinal models will be fit for all outcomes (physical function, knee OA symptomatic burden, balance, muscle strength, cardiorespiratory fitness, and body composition) using all available data with linear mixed models. Mixed models allow for inclusion of all observed outcome data for each participant under the assumption that any missing data are missing at random. No missing data will be imputed. Separate models will be fit for each outcome with no adjustments for multiple comparisons since this is an exploratory proof-of-concept study; however, data from all outcomes assessed will be reported regardless of "significance". For each model, fixed effects will include visit, gender, baseline BMI, age, and severity of baseline OA symptoms. Additionally, if at least 10% of participants are not using prescribed pain medications at each time point, we will include dichotomous use of pain medication as a time-dependent fixed effect. Each model will also include random participant effects to account for correlation between repeated outcome measurements. For each outcome, we will use the model to estimate the mean change from baseline to each follow-up visit along with 95% confidence intervals.

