## Power and Sample Size.

For this study, we chose the 40 m fast-paced walk test as our primary measure of physical function on which to base power calculations based on recent recommendations. We assume that the standard deviation for walk times is 10 seconds, based on results from a study among patients with knee OA; in this study, the estimated standard deviation was 9.2 seconds, and we computed an upper 80% confidence bound of 10 seconds. We further assume that loss at 12 weeks would be at most 10%, and that correlation between repeated outcomes from the same participant would be at least 0.6 (a conservative value). Under these assumptions, enrolling 30 participants would provide at least 80% power to detect a mean 5-second difference between baseline and the 12-week assessment using a two-sided test at the 5% level.

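### Participants may decline or stop any test they expect not to tolerate; this makes the missing-at-random assumption doubtful, and the plan neither tests it nor records the reason

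*Combined protocol and SAP*

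**What the plan says.** Under Enhancing Participants Understanding of the Study, the protocol covers all clinical and functional assessments: "participants may choose not to engage in a particular assessment if they anticipate it will not be tolerable". The same sentence lets a participant break off a test that has already begun. Neither right is limited to a particular visit, so both apply at baseline, week 6 and week 12.

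Under Aim 2 Analyses, every outcome is analysed "using all available data with linear mixed models", "under the assumption that any missing data are missing at random". The section adds: "No missing data will be imputed". On covariates, "fixed effects will include visit, gender, baseline BMI, age, and severity of baseline OA symptoms". Dichotomous pain-medication use may be added as a time-dependent effect if a 10% condition is met. A separate model is fitted for each outcome.

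On reasons for missing data, the retention section says: "Frequency and reasons for initial refusal, ineligibility, and drop out will be collected". The Aim 1 paragraph after the project timeline says the same. A single test missed at an attended visit is not on that list. The documents give no score for a declined or stopped test and no analysis under any other missing-data assumption.

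**The concern.** The stated ground for declining is expected intolerance, which may well be related to how the participant would have performed. If someone skips the week-12 walk or stair climb because the knee is worse at week 12, missingness depends on the value not seen. The model cannot recover that. Its covariates are baseline ones apart from visit and, possibly, pain medication. Because each outcome is modelled separately, WOMAC pain at the same visit does not inform the walk model.

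The study has no control arm in which similar skipping might offset the shift. A result judged well tolerated and promising is meant to support a large randomized trial, and the outcomes are meant to help choose that trial's measures. Which tests patients cannot tolerate is therefore useful Aim 1 information. A participant who attends week 12 but declines the stair climb counts as retained, so the planned summaries would not show it.

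**Working it through.** **Inputs from Power and Sample Size:** SD 10 s, within-participant correlation ρ = 0.6, change of 5 s in 40 m walk time, 30 enrolled, at most 10% lost, two-sided 5% test. **Assumed, because the documents give no figure:** skip rates of 5%, 10% and 20%.

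**Step 1: the plan's own figure.** The plan states that "enrolling 30 participants would provide at least 80% power". SD of change = 10 × √(2 × (1 − 0.6)) = 8.94 s. Completers = 30 × 0.9 = 27. Noncentrality = 5 / (8.94/√27) = 2.90. Power is 79.8% by the paired t test and 82.8% by the normal approximation, so the statement reproduces to rounding. The 10% loss is its only allowance for missing data.

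**Step 2: the slowest skip week 12 because of their week-12 time.** If the slowest fraction r is missing, the mean of the observed week-12 times falls by δ = 10 × φ(z) / (1 − r), where z is the upper-r normal point. A random-intercept model with three visits corrects part of this from baseline and week 6. The regression weight on each is ρ/(1 + ρ) = 0.6/1.6 = 0.375, and the observed group's mean on each of those visits is lower by ρδ = 0.6δ. The bias that remains is −δ + 2 × 0.375 × 0.6δ = −0.55δ.

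- 5%: δ = 10 × 0.1031/0.95 = 1.09 s; bias −0.6 s
- 10%: δ = 10 × 0.1755/0.90 = 1.95 s; bias −1.1 s
- 20%: δ = 10 × 0.2800/0.80 = 3.50 s; bias −1.9 s

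**Step 3: other mechanisms.** These come from a large-sample simulation with the same random-intercept covariance, variance components held at their true values and no covariates. It agrees with Step 2 to within 0.1 s. Negative means the estimate moves towards improvement.

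| Who skips | 5% | 10% | 20% |
|---|---|---|---|
| Slowest at week 12 skip week 12 | −0.6 s | −1.1 s | −1.9 s |
| Same, weaker dependence (logistic, slope 1 per SD) | −0.3 s | −0.5 s | −1.0 s |
| Slowest at each follow-up skip that follow-up | −0.7 s | −1.2 s | −2.2 s |
| Week-12 skipping follows observed baseline time | 0.0 s | 0.0 s | 0.0 s |
| Slowest skip baseline only | +0.6 s | +1.1 s | +1.9 s |
| One tolerance limit at every visit, true improvement 5 s (rate is that at baseline) | +0.4 s | +0.7 s | +1.1 s |
| Same people skip every visit | 0.0 s | 0.0 s | 0.0 s |

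The baseline-only row mirrors Step 2: the same 0.55δ falls on the baseline mean, so the change moves the other way.

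**Step 4: effect on a test when nothing has changed.** With 30 participants, no true change and the slowest skipping week 12, a paired t test on completers rejects about 8% of the time if 3 skip and 12% if 6 skip, against a nominal 5%. This is a completers' test, not the planned mixed model, so it is only indicative.

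**The case against.** The strongest reply is that the protocol grants a right and does not describe a missingness mechanism. Skipping that follows earlier scores or covariates in the model is compatible with missing at random, and the table shows no bias in that case. This stands. A reader might infer that the opt-out contradicts the plan's assumption, but the documents do not support that.

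A reader might also infer that results are biased towards improvement. That does not follow either, because the right applies at baseline too and several plausible patterns push the other way or cancel.

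A third inference is that the opt-out hides harm. The plan has other routes for harm: adverse-event reporting, a study hold after two moderate or severe events, pain scores during and after exercise, completed bouts, mode changes, and the WOMAC, a questionnaire that is unlikely to be physically intolerable. What can be lost is the change in the performance tests, not sight of the participant.

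The skip rate is assumed, and the largest figures come from the harshest mechanism, in which exactly the slowest skip. The eligibility criteria exclude people unable to ride a stationary bike and those waiting for joint replacement, which makes high rates less likely for a 40 m walk. The study is also labelled exploratory and reports every outcome. These points limit the consequence without removing it.

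Finally, case report forms and the manual of procedures are mentioned but are not in the text reviewed, and may already hold a reason code. A code alone would not supply the missing analysis.

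**Conclusion.** The point holds in a limited form. A procedure in the protocol makes missing at random doubtful for the performance tests. The plan has no analysis that tests the assumption, and the reviewed text records no reason for a skipped test.

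Under the plan's SD and correlation and assumed skip rates of 5% to 20%, the week-12 walk-time improvement is overstated by about 0.6 to 2.2 s if the slowest skip at follow-up (12% to 44% of the 5 s target), or by 0.3 to 1.0 s under weaker dependence. It is unbiased if skipping follows observed baseline times. It is understated by about 0.4 to 1.9 s if the slowest skip baseline only, or if one tolerance limit applies throughout and participants truly improve by 5 s. Neither the direction nor the rate can be known from the documents. That is the reason to record why a test was not done. This is an inexpensive improvement worth making, not a fault that invalidates the analysis.

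**What to change.** Keep the participant's right to decline or stop. At every visit, including baseline, code each untaken or stopped test as either declined or stopped for intolerance, or other missing. Tabulate the counts by test and visit as part of Aim 1.

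Keep the Aim 2 mixed model as the main analysis. Add one prespecified sensitivity analysis for the function tests, in one of two forms:

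- score intolerance as a poor result at all visits: 0 for the chair stand and the slowest observed time for timed tests; or
- apply a stated range of delta shifts to the values missing for intolerance.

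Report whether the direction of the week-12 change holds. If ranks are used, analyse them with a rank-based paired test, because worst ranks have no place in a linear mixed model in seconds.

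The cost is one form code, a little programming and possibly a less favourable supporting estimate. There is also a real downside: scoring a cautious but capable person who declines at baseline as a poor performer would inflate improvement. The added analysis should therefore stay supportive.

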# Identifying Potential Problems

The Principal Investigators, with the assistance and advice of Research Assistants and Co-Investigators, will be responsible for monitoring participant recruitment and retention throughout the duration of the research study. The Principal Investigators will assess recruitment rates and retention rates each month and determine any potential problems. The Principal Investigators and Co-Investigators will also determine key retention factors that should be emphasized in order to maximize participant retention throughout the duration of the study. In the event retention issues arise throughout the study the Principal Investigators, with advice from Co-Investigators, will develop new intervention strategies to maximize participant retention and revise the MOOP as necessary. Drs. [name] and [name] currently have weekly communications, providing a foundation for timely interaction and trouble-shooting of issues that may arise. Problems requiring immediate attention of the research lab team will be communicated by [name].

# Monetary Compensation

Participants will be paid to help compensate for their time and travel. Participants will receive a total of \$100. Payments will be prorated; \$14.00 for pre-testing and post-testing, respectively; a total of \$6.00 per week of completed training will also be provided. There will also be free parking provided for testing and training purposes.

# Participant Screening and Eligibility Criteria

# **Participant Screening**

Individuals interested in the study will be screened for eligibility criteria via telephone, reducing the chance of participants coming to the lab for lab screening if they would be excluded based upon demographic factors or level of physical function, which have been outlined in the exclusion criteria. Individuals who meet eligibility criteria and are interested in participating will meet a study team member to complete informed consent and inclusion criteria. All potential patients will undergo a 12-lead electrocardiogram and will be cleared to participate following medical history review from Drs. [name] and [name]. Following clearance, baseline testing will occur.

Thirty patients with symptomatic knee OA will be recruited, which we will define as a diagnosis of knee OA and current knee symptoms in at least one knee. Patients with physician diagnoses of knee OA will be identified from University of North Carolina (UNC) electronic medical records. For current joint symptoms, participants must have a minimum score of 6 out of 20 on the Western Ontario and McMasters Universities Osteoarthritis Index (WOMAC), pain subscale. We will include participants 40-75 years old with body mass index of 18.5-50 kg/m2 because: 1) knee OA onset typically begins after age 40 and is more common with greater obesity, and 2) HIIT is well-tolerated in middle-aged to older adults who are normal weight, overweight, obese,

and morbidly obese. Inclusion of these participants will improve generalizability of study results to real-world patients.

We will aim to ensure that participant selection is equitable and all relevant demographic groups have access to study participation by contacting (via initial letter and telephone call) all participants who meet inclusion / exclusion criteria, regardless of demographic characteristics. We have also aimed to produce recruitment and intervention materials that are appropriate for individuals with low literacy or education levels. We will continue to recruit participants until we reach our sample size goal of N=30.

Interactions with participants during the recruitment process will include both telephone and in-person interaction. When study teams are speaking with participants via telephone (e.g., recruitment/screening call or when participants call to self-refer for the study), this will be done in a private location. In-person baseline visits, which will include giving information about the study so participants can decide whether to participate, will also be conducted in private locations.

The list of potential study participants, based on medical record review, will be transferred into a secure computerized tracking database. Likewise, participant data for all participants enrolled in the study will be entered into a secure computerized enrollment log. These data will be accessible only to study personnel needing access to fulfill their study related duties.

# **Eligibility Criteria**

All participants must meet the following criteria:

- Between the ages of 40 and 75 years old
- Body mass index of 18.5-50 kg/m^2
- Exhibits symptomatic knee OA, defined as a diagnosis of knee OA, as identified from UNC electronic medical records, and current knee symptoms in at least one knee, having a minimum score of 6 out of 20 on the Western Ontario and McMasters Universities Osteoarthritis Index (WOMAC) pain subscale.

Potential participants meeting any of the following criteria (based on the electronic medical record or in laboratory screening) will be excluded if:

- Individuals diagnosed with a cardiovascular condition restricting exercise
- Individuals currently meeting Department of Health and Human Services Guidelines for physical Activity (≥ 150 minutes per week)
- Individuals currently doing HIIT
- Individuals currently participating in physical therapy for knee OA
- Individuals currently participating in another OA intervention study
- Received a corticosteroid or hyaluronic acid intra-articular injection involved in the knee in the previous 3 weeks or scheduled for during the intervention
- Diagnosis of gout in the knee
- Diagnosis of Rheumatoid arthritis
- Diagnosis of Fibromyalgia
- Other systemic rheumatic disease
- Severe dementia or other memory loss

- Active diagnosis of psychosis or uncontrolled substance abuse disorder
- Hospitalization for a stroke, heart attack, or heart failure, or had surgery for blocked arteries in the past 3 months
- Total joint replacement knee surgery, other knee surgery, meniscus tear, or ACL tear in the past 6 months
- On a waiting list for total joint replacement
- Severely impaired hearing or speech
- Pregnant or planning to become pregnant while enrolled in the study
- Inability to speak English
- Serious or terminal illness as indicated by referral to hospice or palliative care
- Nursing home residence
- Inability to ride a stationary bike
- Any other health problems that would prohibit safe participation in the study.

Use and changes of medications for OA will be monitored and recorded during the study but will not be a reason for exclusion. Participants will be withdrawn if they develop any new health problems or other events that would either a) make participation in the study intervention or measures unsafe or b) confound study outcomes. These largely mirror study exclusion criteria and are as follows:

- new diagnosis of rheumatoid arthritis, fibromyalgia, or other systemic rheumatic disease
- new diagnosis of dementia or other memory loss condition with symptoms significant enough to impede ongoing study participant
- new diagnosis of psychosis or current uncontrolled substance abuse disorder
- total joint replacement (knee or hip) surgery, other significant knee or hip surgery, or ACL tear
- serious/terminal illness as indicated by referral to hospice or palliative care
- other health problem that would prohibit participation in the study

